5.3 Lifestyle restrictions

The following restrictions apply while the patient is receiving durvalumab and for the specified times before and after:

1. Female patient of childbearing potential
 - Female patients of childbearing potential who are not abstinent and intend to be sexually active with a non-sterilized male partner, must use at least 1 **highly** effective method of contraception (Table 5) from the time of screening throughout the total duration of the drug treatment and the drug washout period (180 days after the last dose of durvalumab + tremelimumab combination therapy or 90 days after the last dose of durvalumab monotherapy). Non-sterilized male partners of a female patient of childbearing potential must use a male condom plus spermicide throughout this period. Cessation of birth control after this point should be discussed with a responsible physician. Periodic abstinence, the rhythm method, and the withdrawal method are not acceptable methods of contraception. Female patients should refrain from breastfeeding throughout this period.
 - Pregnancy testing will be performed according to the schedule of activities (SoA) (Table 1, Table 2, and Table 3).
2. Male patients with a female partner of childbearing potential
 - Non-sterilized male patients who are not abstinent and intend to be sexually active with a female partner of childbearing potential, must use a male condom plus spermicide from the time of screening throughout the total duration of the drug treatment and the drug washout period (180 days after the last dose of durvalumab + tremelimumab combination therapy or 90 days after the last dose of durvalumab monotherapy). Periodic abstinence, the rhythm method, and the withdrawal method are not acceptable methods of contraception. Male patients should refrain from sperm donation throughout this period.
 - Female partners (of childbearing potential) of male patients must also use a highly effective method of contraception throughout this period (Table 5).

Please note, females of childbearing potential are defined as those who are not surgically sterile (ie, bilateral salpingectomy, bilateral oophorectomy, or complete hysterectomy) or postmenopausal.

Women will be considered postmenopausal if they have been amenorrheic for 12 months without an alternative medical cause. The following age-specific requirements apply:

- Women <50 years of age would be considered postmenopausal if they have been amenorrheic for 12 months or more following cessation of exogenous hormonal treatments and if they have luteinizing hormone and follicle-stimulating hormone levels in the postmenopausal range for the institution.

- Women ≥ 50 years of age would be considered postmenopausal if they have been amenorrheic for 12 months or more following cessation of all exogenous hormonal treatments, had radiation-induced menopause with last menses >1 year ago, had chemotherapy-induced menopause with last menses >1 year ago.
- Women who are surgically sterile (ie, bilateral salpingectomy, bilateral oophorectomy, or complete hysterectomy) are eligible.

Highly effective methods of contraception defined as one that results in a low failure rate (ie, less than 1% per year) when used consistently and correctly are described in Table 5. Note that some contraception methods are not considered highly effective (eg, male or female condom with or without spermicide; female cap, diaphragm, or sponge with or without spermicide; non-copper containing intrauterine device; progestogen-only oral hormonal contraceptive pills where inhibition of ovulation is not the primary mode of action [excluding Cerazette/desogestrel which is considered highly effective]; and triphasic combined oral contraceptive pills).

Table 5 Highly effective methods of contraception (<1% failure rate)

Barrier/intrauterine methods	Hormonal methods

 • Copper T intrauterine device • Levonorgestrel-releasing intrauterine system (eg, Mirena®)^a 	
 • Implants: Etonogestrel-releasing implants (eg, Implanon® or Norplant®) • Intravaginal Devices: Ethinylestradiol/etonogestrel-releasing intravaginal devices (eg, NuvaRing®) • Injection: Medroxyprogesterone injection (eg, Depo-Provera®) • Combined Pill: Normal and low dose combined oral contraceptive pill • Patch: Norelgestromin/ethinylestradiol-releasing transdermal system (eg, Ortho Evra®) • Minipill: Progesterone-based oral contraceptive pill using desogestrel: Cerazette® is currently the only highly effective progesterone-based pill

^a This is also considered a hormonal method.

3. For patients randomized to receive SoC treatment in parent protocols, follow the local prescribing information relating to contraception, the time limit for such precautions, and any additional restrictions for agents in the SoC treatment regimen.
4. All patients: Patients should not donate blood or blood components while participating in this study and through 180 days after receipt of the final dose of durvalumab combination therapy or 90 days after receipt of the final dose of durvalumab or until alternate anticancer therapy is started.
5. Restrictions relating to concomitant medications are described in Section 6.4.

5.4 Screen failures

Screen failures are patients who do not fulfill the eligibility criteria for the study. These patients should have the reason for study withdrawal recorded as “eligibility criteria not fulfilled” (ie, patient does not meet the required inclusion/exclusion criteria). This reason for study withdrawal is only valid for screen failures (ie, not enrolled patients).

A minimal set of screen failure information is required to ensure transparent reporting of screen failure patients to meet the Consolidated Standards of Reporting Trials publishing requirements and to respond to queries from regulatory authorities. Minimal information includes demography, screen failure/non-enrollment details, eligibility criteria, and any SAEs.

6. STUDY TREATMENTS

Study treatment is defined as any IP (including marketed product comparator and placebo) or medical device(s) intended to be administered to a study participant according to the study protocol. Study treatment in this study refers to durvalumab monotherapy.

6.1 Treatments administered

6.1.1 Investigational product

AstraZeneca will supply durvalumab (MEDI4736). All patients in Cohort 1 will receive durvalumab monotherapy at the dosing regimen described below (Table 6). While patients in Cohort 2 are all eligible for retreatment with durvalumab, some may never receive treatment. Patients who were previously administered durvalumab at a dose regimen different from the regimen described for the present study will switch to the dose regimen described below. Only 1 course of retreatment is allowed (inclusive of any retreatment in the parent clinical study). Patients enrolled in Cohort 3 will not receive any study drug.

Table 6 Study treatment

	Treatment
Study treatment name:	Durvalumab (MEDI4736)
Dosage formulation:	500-mg vial solution for infusion after dilution, 50 mg/mL
Route of administration:	Intravenous (IV)
Dose:	1500 mg
Dosing instructions:	A dose of 1500 mg will be delivered through an IV administration set with a 0.2 µm or 0.22 µm filter. If a patient’s weight falls to 30 kg or below (≤ 30 kg), then the patient should receive weight-based dosing equivalent to 20 mg/kg of durvalumab q4w until weight improves to above 30 kg (>30 kg).
Packaging and labeling:	Study drug will be provided in vials. Each vial will be labeled in accordance with Good Manufacturing Practice Annex 13 and per country regulatory requirement. ^a
Frequency:	Every 4 weeks
Manufacturer:	MedImmune
Provider:	AstraZeneca

^a Label text prepared for durvalumab (MEDI4736) will show the product name as “MEDI4736” or “durvalumab (MEDI4736)” depending upon the agreed product name used in the approved study master label document. All naming conventions are correct during this transitional period.

6.1.1.1 Durvalumab (MEDI4736)

Durvalumab (MEDI4736) will be supplied by AstraZeneca as a 500-mg vial solution for infusion after dilution. The solution contains 50 mg/mL durvalumab (MEDI4736), 26 mM histidine/histidine-hydrochloride, 275 mM trehalose dihydrate, and 0.02% weight/volume (w/v) polysorbate 80; it has a pH of 6.0 and density of 1.054 g/mL. The nominal fill volume is 10.0 mL. IP vials are stored at 2°C to 8°C (36°F to 46°F) and must not be frozen. Drug product should be kept in original packaging until use to prevent prolonged light exposure.

Preparation of durvalumab (MEDI4736) doses for administration with an IV bag

The dose of durvalumab (MEDI4736) for administration must be prepared by the Investigator’s or site’s designated IP manager using aseptic technique. Total time from needle puncture of the durvalumab (MEDI4736) vial to the start of administration should not exceed:

- 24 hours at 2°C to 8°C (36°F to 46°F)

- 4 hours at room temperature

A dose of 1500 mg will be administered using an IV bag containing 0.9% (w/v) saline or 5% (w/v) dextrose, with a final durvalumab (MEDI4736) concentration ranging from 1 to 15 mg/mL and delivered through an IV administration set with a 0.2- or 0.22- μ m filter. Add 30.0 mL of durvalumab (MEDI4736) (ie, 1500 mg of durvalumab [MEDI4736]) to the IV bag. The IV bag size should be selected such that the final concentration is within 1 to 15 mg/mL. Mix the bag by gently inverting to ensure homogeneity of the dose in the bag.

If patient weight falls to ≤ 30 kg, WT-based dosing at 20 mg/kg will be administered using an IV bag containing 0.9% (w/v) saline or 5% (w/v) dextrose, with a final durvalumab (MEDI4736) concentration ranging from 1 to 15 mg/mL and delivered through an IV administration set with a 0.2- or 0.22- μ m filter.

Standard infusion time is one hour; however, if there are interruptions during the infusion, the total allowed infusion time should not exceed 8 hours at room temperature.

Do not co-administer other drugs through the same infusion line.

The IV line will be flushed with a volume of IV diluent equal to the priming volume of the infusion set used, after the contents of the IV bag are fully administered, or complete the infusion according to institutional policy to ensure the full dose is administered.

If either preparation time or infusion time exceeds the time limits, a new dose must be prepared from new vials. Durvalumab (MEDI4736) does not contain preservatives and any unused portion must be discarded.

[figure not shown]
6.1.2 Dose and treatment regimen

6.1.2.1 Durvalumab (MEDI4736) monotherapy

Patients who receive durvalumab monotherapy treatment (Cohort 1) or durvalumab monotherapy retreatment (Cohort 2) will receive 1500 mg durvalumab via IV infusion q4w, until PD is determined by the Investigator following RECIST v1.1, unless there is unacceptable toxicity, withdrawal of consent, or another discontinuation criterion is met. See [Figure 2](#) (Please note, if a patient's weight falls to 30 kg or below, the patient should receive WT-based dosing equivalent to 20 mg/kg of durvalumab q4w after consultation between the Investigator and Study Physician, until the weight improves to >30 kg).

The standard infusion time is 1 hour; however, if there are interruptions during infusion, the total allowed time should not exceed 8 hours at room temperature.

Figure 2 Durvalumab monotherapy dosing schedule

Q4W every 4 weeks.

6.1.3 Duration of treatment and criteria for treatment through progression and for retreatment

All durvalumab treatment will be administered beginning on Day 1 (Cohort 1) or Day 1 retreatment (Cohort 2), until progression as determined by the Investigator using RECIST v1.1 (refer to [Appendix C](#)), unless there is unacceptable toxicity, withdrawal of consent, or another discontinuation criterion is met.

Patients receiving durvalumab who experience PD and, in the Investigator’s opinion, continue to receive benefit from their assigned treatment may continue to receive durvalumab for as long as they meet specific clinical criteria and are deriving clinical benefit in the opinion of the Investigator. For all patients who are treated through PD, the Investigator should ensure patients still meet all of the inclusion criteria and none of the exclusion criteria for this study and obtain additional informed consent for continuation of treatment. The treatment ICF will specify that treatment beyond initial evidence of PD is not the standard of care and that alternative treatment options, either locally licensed treatments or other clinical trials, are potentially available for this patient population.

Patients with rapid tumor progression or with symptomatic progression, that require urgent medical intervention (eg, central nervous system metastasis, respiratory failure due to tumor compression, or spinal cord compression) will not be eligible for continuing durvalumab (refer to [Appendix C](#)).

For all patients who are continuously treated through progression and for patients who are restarting durvalumab monotherapy, the Investigator should ensure that:

- The patient does not have any significant, unacceptable, or irreversible toxicities, that indicate continuing treatment will not further benefit the patient. The patient may not have experienced a toxicity that required permanent discontinuation of study treatment.

- There is absence of clinical symptoms or signs indicating clinically significant disease progression accompanied by a decline in WHO/ECOG PS to >2
- There is absence of rapid disease progression or threat to vital organs or critical anatomical sites (eg, central nervous system metastasis, respiratory failure due to tumor compression, or spinal cord compression) requiring urgent alternative medical intervention
- The patient still fulfills the eligibility criteria for this study (see Sections 5.1 and 5.2). Patients must also agree to consenting to restart durvalumab monotherapy.
- The patient has not received an intervening systemic anticancer therapy after their assigned treatment discontinuation from the parent study

The patient has had a retreatment baseline tumor assessment within a maximum of 28 days prior to restarting durvalumab (Cohort 2). In Cohort 1, patients will continue with durvalumab monotherapy at 1500 mg q4w until disease progression as confirmed by the Investigator following RECIST v1.1.

During the retreatment period in Cohort 2, eligible patients will resume durvalumab dosing at 1500 mg q4w until disease progression as determined by the Investigator following RECIST v1.1.

Patients who the Investigator determines may not continue treatment after PD will be followed up for OS, and are no longer eligible for retreatment. Patients who have discontinued treatment due to toxicity or symptomatic deterioration, or who have commenced subsequent anticancer therapy, will be followed for OS until withdrawal of consent or death. Upon discontinuation of durvalumab, patients may receive any subsequent anticancer therapy at the discretion of the Investigator.

6.1.4 Storage

The Investigator, or an approved representative (eg, pharmacist), will ensure that all IP is stored in a secured area, in refrigerated temperatures (2°C to 8°C) and in accordance with applicable regulatory requirements. A temperature log will be used to record the temperature of the storage area. Temperature excursions outside the permissible range listed in the clinical supply packaging are to be reported to the monitor upon detection. A calibrated temperature monitoring device will be used to record the temperature conditions in the drug storage facility. Storage conditions stated in the IB may be superseded by the label storage.

6.2 Measures to minimize bias: randomization and blinding

Not applicable.

6.3 Treatment compliance

Study measures will be taken to ensure to document durvalumab treatment compliance, with dates of administration, dosing information, and any safety events related to medication administration will be captured in the study database. Collection and reporting of durvalumab overdoses are summarized in Section 8.4.3.

The administration of all IPs should be recorded in the appropriate sections of the electronic case report form (eCRF).

Any change from the dosing schedule, dose delays/interruptions, and dose discontinuations should be recorded in eCRF. Dose reductions are not allowed.

The IP Storage Manager is responsible for managing the IP from receipt by the study site until the destruction or return of all unused IP.

6.4 Concomitant therapy

The Investigator must be informed as soon as possible about any medication taken from the time of enrollment until the end of the durvalumab treatment, including the 90-day follow-up period following the last dose of study drug. This applies only for patients receiving durvalumab through 90 days after the last dose, and does not apply to patients from Cohort 2 who are not retreated and patients in Cohort 3. No restrictions apply to patients off treatment who are over 90 days from their last dose of durvalumab.

Any medication or vaccine including over-the-counter or prescription medicines, vitamins, and/or herbal supplements that the patient is receiving at the time of enrollment or receives during the study must be recorded along with:

- Reason for use
- Dates of administration including start and end dates
- Dosage information including dose, unit, and frequency

Patients must be instructed not to take any medications, including over-the-counter products, without first consulting with the Investigator.

Restricted, prohibited, and permitted concomitant medications are described in the following tables. Refer also to the Dosing Modification and Toxicity Management Guidelines (see Annex 1).

Table 7 Prohibited concomitant medications

Prohibited medications/class of drug:	Usage:
Cohort 1 and retreated patients in Cohort 2, only	
Any investigational anticancer therapy other than those under investigation in this study	Should not be given concomitantly while the patient is on study treatment
Monoclonal antibodies against CTLA-4, PD-1, or PD-L1 other than those under investigation in this study	Should not be given concomitantly while the patient is on study treatment
Any concurrent chemotherapy, radiotherapy, immunotherapy, or biologic or hormonal therapy for cancer treatment other than those under investigation in this study	Should not be given concomitantly while the patient is on study treatment. (Concurrent use of hormones for non-cancer-related conditions [eg, insulin for diabetes and hormone replacement therapy] is acceptable. Local treatment of isolated lesions, excluding target lesions, for palliative intent is acceptable [eg, by local surgery or radiotherapy].)
Immunosuppressive medications including, but not limited to, systemic corticosteroids at doses exceeding 10 mg/day of prednisone or equivalent, methotrexate, azathioprine, and tumor necrosis factor- α blockers	Should not be given concomitantly or used for premedication prior to the immuno-oncology infusions. The following are allowed exceptions: 
 • Use of immunosuppressive medications for the management of IP-related AEs • Use in patients with contrast allergies • In addition, use of inhaled, topical, and intranasal corticosteroids is permitted A temporary period of steroids will be allowed if clinically indicated and considered to be essential for the management of non-immunotherapy related events experienced by the patient (eg, chronic obstructive pulmonary disease, radiation, nausea, etc).
Herbal and natural remedies which may have immune-modulating effects	Should not be given concomitantly unless agreed by the Sponsor.
Cohorts 1 to 3	
Live attenuated vaccines	Should not be given within 30 days prior to the first dose of IP in the present study and through 90 days after the last dose of IP.
Drugs with laxative properties and herbal or natural remedies for constipation	Should be used with caution through 90 days after the last dose of tremelimumab during the study, if the patient received combination therapy of tremelimumab and durvalumab in the parent clinical study.
Sunitinib	Should not be given concomitantly or through 90 days after the last dose of tremelimumab (acute renal failure has been reported with combination therapy of tremelimumab and sunitinib)

Prohibited medications/class of drug:	Usage:
Epidermal growth factor receptor (EGFR) tyrosine kinase inhibitors (TKIs)	Should not be given concomitantly. Should be used with caution in the 90 days post last dose of durvalumab. Increased incidences of pneumonitis (with third generation EGFR TKIs) and increased incidence of transaminase increases (with first generation EGFR TKIs) has been reported when durvalumab has been given concomitantly.

AE adverse event; CTL cytotoxic T-lymphocyte-associated; EGFR epidermal growth factor receptor; IP investigational product; TKI tyrosine kinase inhibitor; PD programmed death

Table 8 Supportive medications

Supportive medications/class of drug:	Usage:
Concomitant medications or treatments (eg, acetaminophen or diphenhydramine) deemed necessary to provide adequate prophylactic or supportive care, except for those medications identified as “prohibited,” as listed above	To be administered as prescribed by the Investigator
Best supportive care (including antibiotics, nutritional support, correction of metabolic disorders, optimal symptom control, and pain management [including palliative radiotherapy to non-target lesions, etc])	Should be used, when necessary, for all patients
Inactivated viruses, such as those in the influenza vaccine	Permitted

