Cohort 3 includes survival follow-up only for patients previously treated with durvalumab monotherapy or durvalumab in combination with any other approved or investigational anticancer agents who are no longer receiving durvalumab and are not eligible to receive retreatment. Safety assessments will be collected among the patients who are within 90 days since last dose of study drug in the parent study. The patients would undergo OS assessments as per the SoA (Table 3) and may receive any subsequent anticancer therapy at the discretion of the Investigator.

For all cohorts, any assessments which are relevant to preservation of patient safety, as scheduled in the parent clinical study, will be conducted and followed up as per the SoA for this study.

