7. DISCONTINUATION OF TREATMENT AND PATIENT WITHDRAWAL

7.1 Discontinuation of study treatment

An individual patient will not receive any further durvalumab monotherapy if any of the following occur in the patient in question:

- Withdrawal of consent from further treatment with IP. The patient is, at any time, free to discontinue treatment, without prejudice to further treatment. A patient who discontinues treatment is normally expected to remain in the study for safety and OS follow-up unless they specifically withdraw their consent to all further participation in any study procedures and assessments (see Section 7.3).
- An AE that, in the opinion of the Investigator or AstraZeneca, contraindicates further dosing.
- Any AE that meets criteria for discontinuation as defined in the Dosing Modification and Toxicity Management Guidelines (see Annex 1) or as defined in the local prescribing information for the agent.
- Pregnancy or intent to become pregnant
- Non-compliance with the study protocol that, in the opinion of the Investigator or AstraZeneca, warrants withdrawal from treatment with IP (eg, refusal to adhere to scheduled visits).
- Initiation of alternative anticancer therapy including another investigational agent
- Disease progression as determined by the Investigator following RECIST v1.1 (refer to [Appendix C](#)) and Investigator determination that the patient is no longer benefiting from treatment with IP.

Upon discontinuation of durvalumab, patients may receive any subsequent anticancer therapy at the discretion of the Investigator and will follow the schedule of activities (SoA) detailed for Cohort 3 for safety and survival follow-up ([Table 3](#)).

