- Must not have required the use of additional immunosuppression other than corticosteroids for the management of an AE >Grade 1, have not experienced recurrence of an AE if re-challenged, and not currently require maintenance doses of >10 mg prednisone or equivalent per day
- Known allergy or hypersensitivity to any of the study drugs or any of the study drug excipients
- **Deviation 2:** Baseline RECIST scan date is greater than 28 days before the date of starting Cycle 1 of retreatment for Cohort 2, during the WAVE study period.
- **Deviation 3:** No baseline RECIST 1.1 assessment on or before the date of starting Cycle 1 of retreatment (Cohort 2), during the WAVE study period.
- **Deviation 4:** Received prohibited concomitant medications (including other anticancer agents). Please refer to the CSP Section 6.4 for those medications that are detailed as being ‘excluded’ from permitted use during the study. This will be used as a guiding principle for the medical data reviewer of all medications prior to database lock.

All the violations and deviations considered only come from WAVE without taking into account data from parent studies. The important subject-level protocol deviations will be listed and summarized by treatment group (study cohort) in the main part of the CSR. All

participants with important protocol deviations will be listed by center, as an appendix. Site level protocol deviations are collected from the CTMS. The important site level protocol deviations will be listed, as an appendix of the CSR.

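### Sunitinib after tremelimumab: Table 7 bars it for 90 days, while five protocol sections allow any anticancer therapy once durvalumab stops

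*Protocol*

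**What the plan says.** **The restriction.** Protocol Section 6.4, Table 7, has one block of rows for Cohort 1 and retreated Cohort 2 patients and a second block for Cohorts 1 to 3. The second block holds two anticancer entries:

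- Sunitinib: "Should not be given concomitantly or through 90 days after the last dose of tremelimumab". The row gives acute renal failure with the tremelimumab combination as its reason.
- EGFR tyrosine kinase inhibitors: "Should not be given concomitantly. Should be used with caution in the 90 days post last dose of durvalumab". The row cites pneumonitis and transaminase increases seen when these drugs were given together with durvalumab.

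The Section 6.4 text adds: "No restrictions apply to patients off treatment who are over 90 days from their last dose of durvalumab".

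**The permission.** Section 7.1 states: "Upon discontinuation of durvalumab, patients may receive any subsequent anticancer therapy at the discretion of the Investigator". The same permission stands in Section 1 (once for each cohort), Section 1.2, Section 4.1 and Section 6.1.3.

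**The consequence in the SAP.** Section 2.2 lists as Deviation 4, among the important protocol deviations: "Received prohibited concomitant medications (including other anticancer agents". It sends the medical data reviewer to protocol Section 6.4 to decide which drugs count. Important subject-level deviations are listed and summarized by cohort in the study report.

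**The concern.** A site with a patient recently off a durvalumab plus tremelimumab regimen gets opposite answers about sunitinib depending on the section it opens. The restriction rests on a toxicity that the protocol itself reports, so a site acting in good faith on Section 7.1 could breach a safety restriction written into Section 6.4.

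The reporting side follows from this. Deviation 4 takes its definition from Section 6.4, so a treatment choice that Section 7.1 allows could be counted as an important deviation. Whether it is counted would depend on how the reviewer reads the protocol.

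**Working it through.** No sample size, power or event figure bears on this point. The check compares current passages, leaving out the amendment log, and then asks how long the two rules can overlap.

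**1. How often the permission appears.** Section 1 has it three times (Cohorts 1, 2 and 3). Sections 1.2, 4.1, 6.1.3 and 7.1 have it once each. That is 3 + 4 = 7 statements in five numbered sections. Each leaves the choice to the investigator. None sets a waiting period, an exception or a reference to Section 6.4 or Table 7. Section 4.1 does cross-refer, but to Section 7.1, which repeats the permission.

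**2. Whether the sunitinib row reaches patients off treatment.** It does, for three reasons.

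- The row covers Cohort 3, and Section 6.1.1 says Cohort 3 receives no study drug.
- The row sets its own post-dose window. The anticancer rows in the other block are confined to the time on study treatment.
- Section 6.4 lifts restrictions for patients more than 90 days from their last durvalumab dose, which implies that some apply before then.

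**3. Whether both drug entries conflict with the permission.**

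| Entry | Strength after the last dose | Clock starts at | Against the permission |
|---|---|---|---|
| Sunitinib | Should not be given, 90 days | Last tremelimumab dose | Contradiction |
| EGFR inhibitors | Caution, 90 days | Last durvalumab dose | Compatible with investigator discretion; cross-reference missing |

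**4. How long the sunitinib conflict can last.** Study treatment in WAVE is durvalumab monotherapy (Section 6), and inclusion criterion 3 requires other anticancer therapy to have ended. Any tremelimumab was therefore given in the parent study. Let g be the days from the last tremelimumab dose to the last durvalumab dose, assumed to be zero or more. The overlap after durvalumab stops is at most max(0, 90 − g) days. For illustration, in steps of the 28-day WAVE cycle:

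- g = 0: 90 − 0 = 90 days
- g = 28: 90 − 28 = 62 days
- g = 84: 90 − 84 = 6 days
- g = 112: 90 − 112 is negative, so no overlap

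In Cohort 3 the part of this window that falls before enrollment also drops out. Cohort 3 patients who enroll soon after a combination regimen are the clearest case, and Section 1 foresees entry within 90 days of the last parent-study dose. A Cohort 1 patient who receives several WAVE cycles leaves the window while still on durvalumab.

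**5. What Deviation 4 would do.** It sets no cohort or time limit of its own but defers to Section 6.4. There the general anticancer rows are already limited to Cohort 1 and retreated Cohort 2 patients on study treatment, so ordinary subsequent therapy is not caught. Sunitinib inside the tremelimumab window is caught. Entries that ask only for caution (EGFR inhibitors after dosing, and laxatives) sit in a table titled as prohibited medications, so their status under Deviation 4 is left to the reviewer.

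**The case against.** The strongest reply is that the conflict is small and largely managed. The permission mandates nothing. Section 6.4 already supplies cohort and time limits for most entries. Deviation 4 uses that section only as a guiding principle, and the medical team reviews and categorizes deviations. All of this stands and keeps the point narrow. It does not remove the sunitinib conflict, because investigator discretion then authorizes a choice that Table 7 says should not be made.

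A second reply is that Section 6.4 exempts Cohort 3, since it says a rule "does not apply to patients from Cohort 2 who are not retreated and patients in Cohort 3". That sentence concerns informing the investigator about medication taken. Table 7 still has rows for Cohort 3, and Table 3 schedules concomitant medication checks for that cohort at days 30, 60 and 90. The sentence adds doubt about scope; it does not settle it.

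Three stronger readings might be inferred, and the documents do not support them:

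- *Every patient within 90 days of stopping durvalumab is affected.* The sunitinib clock runs from tremelimumab, so patients who never had tremelimumab, or whose 90 days have passed, are outside it.
- *EGFR inhibitors are both barred and allowed after durvalumab.* After the last dose the table says only "Should be used with caution in the 90 days post last dose of durvalumab", and the toxicities it cites arose with concomitant use.
- *The primary safety summary becomes uninterpretable.* Protocol Section 9.3.3.1 flags adverse events that occur after subsequent anticancer therapy. The SAP has an eCRF module for that therapy (Section 4) and a summary of it by cohort (Section 5.2.9), so such events can be identified.

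**Conclusion.** The point holds in a narrow form. Current protocol text contradicts itself on sunitinib for patients who are off durvalumab and within 90 days of a parent-study tremelimumab dose, and SAP Deviation 4 inherits the contradiction. The number of such patients, and of those for whom sunitinib would be considered, is not in the documents. The overlap lasts at most 90 days after durvalumab stops, and less or nothing where durvalumab continued after tremelimumab. That bound assumes that the last durvalumab dose did not precede the last tremelimumab dose.

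No estimate or analysis set changes. What is affected is site conduct under a restriction that cites acute renal failure, and the classification of a few possible deviations. The EGFR inhibitor entry needs only a cross-reference. Which rule should govern is a clinical decision that this review does not take.

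**What to change.** 1. **Protocol.** Reconcile the permission in Sections 1, 1.2, 4.1, 6.1.3 and 7.1 with the post-dose entries of Table 7, so that one rule applies to a patient off durvalumab. The text can be aligned at either end: in the permission sentences or in the table. The sponsor's medical team must decide which rule stands. Include a cross-reference for the EGFR inhibitor entry.
2. **SAP Section 2.2, Deviation 4.** State that a medication counts as prohibited only within the cohort and time window of its Section 6.4 entry, and that entries asking only for caution are not counted as deviations.

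The cost is amendment wording, a memo to sites and a short addition to the SAP. No new data, visits or procedures are needed.
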